#### **4.3 Inclusion Criteria**

[figure not shown]
4. Patients identified through the algorithm as described at paragraph 4.1;
5. Male or female;
6. At least 18 years at date of first index hospitalization;

#### **4.4 Exclusion criteria**

The subjects who lives outside the regional territory of competence will be excluded from analysis due to the difficulty in obtaining the medical data.

## **5 STUDY PROCEDURES AND DATA COLLECTION**

To evaluate primary objective of the study, patient information will be obtained only from regional administrative databases both for out-patient and in-patient settings. These data will be related only to the year 2017.

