## **3. STUDY DESIGN**

This is a multi-center, observational study involving retrospective collection of NSCLC patients information. All consecutive patients who had a newly diagnosis of NSCLC in 2017 from healthcare administrative database and received at least one anti-cancer drug treatment between January 2017 and December 2017, identified through the proposed algorithm, will be considered. All data needed for KPI calculation, even if they fall outside January-December 2017 period, will be collected. The end of data collection will be defined as patient death or 30 June 2018, whichever came first.

A set of potential KPIs had been developed from a panel of experts (clinicians, IT experts etc..) to investigate the appropriateness of activities within NSCLC care pathway, with a special focus on the use of immunotherapy.

The eligible population and data will be gathered retrospectively through an algorithm from administrative databases (SDO, REM, ASA, FED, AFT, ADI, SDHS-hospice).

Administrative data will be used as unique resource:

- to identify patients cohort;
- to measure KPIs along care pathway ;

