### 5.1 Clinical variables of interest for the study

The only source for clinical information will be administrative databases in all its parts.

[figure not shown]
We will focus primarily on the following set of clinical data:

- Biopsy at diagnosis;
- Presence of metastatic NSCLC at diagnosis;
- Neoadjuvant treatment before lung cancer surgical resection;
- Lung cancer main surgical resection;
- Length of stay in hospital after lung major surgery;
- Main information regarding anti-cancer drug treatments at the first diagnosis and for subsequent lines
- Multidisciplinary team (MDT) meeting discussion;
- Radiotherapy (RT) in the end of life;
- Death;
- Integrated home care utilization;
- Hospice care utilization.

[figure not shown]

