### 5.2 Key performance indicators for monitoring care pathway in NSCLC patients

The following key performance indicators (KPIs) will be measured to investigate the appropriateness of NSCLC patient care pathways, with a special focus on the use of immunotherapy.

[figure not shown]
BOZZA - KPI -	
1	
Percentage of patients who performed biopsy within 7 days from the date of examination prescription
 
NUM: Number of patients who performed biopsy within 7 days from prescription; DEN: Total number of patients identified by the algorithm who performed biopsy;

2	
Percentage of mNSCLC patients at diagnosis
 
NUM: Number of patients with metastases (presence of one of the following codes (197*,198*,199*) in all position of diagnosis codes for index hospitalization); DEN: Total number of patients identified by the algorithm;

3	
Percentage of major surgical resections within the year of analysis.
 
NUM: Number of patients who underwent to lung cancer major surgical resection; DEN: Total number of patients identified by the algorithm;

	
To identify major surgical procedures for lung, the following codes of ICD-9-CM classification will be identified:
 
  
 ICD-9-CM coding related to major surgery on lung	
   
 32.01	ENDOSCOPIC EXCISION OR DESTRUCTION OF LESION OR TISSUE OF BRONCHUS	
 
 32.29	OTHER LOCAL EXCISION OR DESTRUCTION OF LESION OR TISSUE OF LUNG	
 
 32.3	SEGMENTAL RESECTION OF LUNG	
 
 32.4	LOBECTOMY OF LUNG	
 
 32.5	COMPLETE PNEUMONECTOMY	
 
 34.6	SCARIFICATION OF PLEURA	
  
	ICD-9-CM coding related to major surgery on lung		32.01	ENDOSCOPIC EXCISION OR DESTRUCTION OF LESION OR TISSUE OF BRONCHUS	32.29	OTHER LOCAL EXCISION OR DESTRUCTION OF LESION OR TISSUE OF LUNG	32.3	SEGMENTAL RESECTION OF LUNG	32.4	LOBECTOMY OF LUNG	32.5	COMPLETE PNEUMONECTOMY	34.6	SCARIFICATION OF PLEURA
ICD-9-CM coding related to major surgery on lung															
32.01	ENDOSCOPIC EXCISION OR DESTRUCTION OF LESION OR TISSUE OF BRONCHUS														
32.29	OTHER LOCAL EXCISION OR DESTRUCTION OF LESION OR TISSUE OF LUNG														
32.3	SEGMENTAL RESECTION OF LUNG														
32.4	LOBECTOMY OF LUNG														
32.5	COMPLETE PNEUMONECTOMY														

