34.6	SCARIFICATION OF PLEURA														
4	
Percentage of surgical patients on the total number of patients with exploratory thoracotomy in inpatient setting.            NUM: Total of patients with only exploratory thoracotomy procedure (Cod 34.02);            DEN: Number of surgical patients;            For major surgery, ICD-9-CM codes were selected as reported for KPI 3.            Surgical patients defined as patients who receive any surgical procedure (major and/or explorative)
														
5	
Percentage of patients undergoing neoadjuvant therapy ( CT or CT+RT within 6 months prior to the first major resection date)            NUM: Number of patients who underwent induction treatment as CT or CT+RT in the 6 months prior to surgery;            DEN: Total number of surgical patients;            The algorithm will not be able to identify patients who received neoadjuvant therapy in clinical trials.            For major surgery, ICD-9-CM codes were selected as reported for KPI 3.
														
6	
30-day mortality rate from major surgery            NUM : Number of patients who died within 30 days from major surgery;            DEN: Total number of surgical patients;            For major surgery, ICD-9-CM codes were selected as reported for KPI 3.
														
7	
Percentage of patients discussed in the multidisciplinary team (MDT) meeting at least once in the year of incidence            NUM: Number of patients discussed at least one time in MDT meetings;            DEN: Total number of patients identified by the algorithm;
														
8	
Percentage of patients who performed imaging exams such as MRI, TC and PET within 7 days from MDT meeting            NUM: Number of patients who performed imaging exams within 7 days from MDT meeting;            DEN : Total number of patients discussed in MDT meeting;
														
9	
Average and range of length of stay calculated as the mean difference among date of discharge and date of admission.
														
10	
Average time between biopsy and the first administration of systematic anti-cancer drug (excluded neoadjuvant patients of KPI 5) calculated as the average difference among biopsy and the first date of administration of chemotherapy.            For patients enrolled in experimental clinical trial will not be possible to retrieve information on therapies from administrative database.
														

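### Section 5 confines the primary-objective data to 2017, while section 3 follows KPI data to death or 30 June 2018; if the extraction followed section 5 literally, KPIs 11b, 15 and 16 would be understated and KPIs 12 and 14 would lose all 2018 deaths

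*Protocol*

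**What the plan says.** Two current sentences of the protocol set the data window for the KPIs, which are the primary objective.

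- Section 5 (Study procedures and data collection), speaking of the patient information used for the primary objective: "These data will be related only to the year 2017".
- Section 3 (Study design): "All data needed for KPI calculation, even if they fall outside January-December 2017 period, will be collected". It continues: "The end of data collection will be defined as patient death or 30 June 2018, whichever came first".

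Section 3 also defines the cohort by year: new diagnoses in 2017 in patients who "received at least one anti-cancer drug treatment between January 2017 and December 2017".

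Section 5.1 lists death and "Main information regarding anti-cancer drug treatments at the first diagnosis and for subsequent lines" among the variables of interest. In section 5.2 only two KPIs name a year in their own definition: KPI 3, "Percentage of major surgical resections within the year of analysis", and KPI 7, "at least once in the year of incidence". The others have a follow-up window (KPI 6: "Number of patients who died within 30 days from major surgery"; KPI 11b: immunotherapy continuing beyond 6 months from first dose), or use deceased patients as the base (KPIs 12 and 14), or count any use with no window at all (KPIs 11a, 15 and 16).

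**The concern.** The study is an extraction from administrative databases with no case report form, so the dates written into the query determine the results. The protocol gives two end dates for the same primary-objective data, 31 December 2017 and 30 June 2018, and no section says which prevails. Two analysts, each following one section, could report different KPI values for the same patients.

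The indicators most exposed are those that need time after treatment starts. They include KPI 11b, although section 5.2 gives immunotherapy a special focus.

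**Working it through.** The protocol gives no figure to reproduce: section 7.2 states that no sample size calculation was made and gives about 400 patients as a feasibility figure. The check is date arithmetic on the two cut-offs.

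**Inputs from the protocol.** Cut-offs 31 December 2017 (section 5) and 30 June 2018 (section 3); at least one drug treatment in 2017 (section 3); KPI windows (section 5.2); N about 400 (section 7.2).

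**Assumptions, not in the protocol.** Index dates uniform over 2017; first drug 30 or 45 days after index and by 31 December 2017; exponential survival with median 6 to 18 months; 6 months = 183 days. With 1 January 2017 as day 0, the cut-offs are days 364 and 545. The drug criterion leaves index days 0-334 (335 days, 30-day lag) or 0-319 (320 days, 45-day lag).

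**KPI 11b.** 31 December 2017 minus 183 days is 1 July 2017, so under section 5 no later first dose can qualify. 30 June 2018 minus 183 days is 29 December 2017. The reading is the true share x (1 - share of starters who cannot be observed long enough). For a true 40%:

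| First immunotherapy dose | Section 5: unobservable | Reads | Section 3: unobservable | Reads |
|---|---|---|---|---|
| Is the first drug | 183/335 = 54.6%; 183/320 = 57.2% | 18.1%; 17.1% | 2/335 or 2/320 = 0.6% | 39.8% |
| 90 days after index | 183/275 = 66.5% | 13.4% | 62/335 = 18.5%; 47/320 = 14.7% | 32.6%; 34.1% |

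**KPIs 12 and 14.** The share dead by cut-off c is the average over eligible start days s of 1 - exp(-h(c - s)), with h = ln 2 / (median in months x 30.4375).

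- Survival counted from index: 32-43% of the deaths seen by 30 June 2018 fall in 2018, over medians of 6 to 18 months. With N = 400 and a 12-month median, 120-124 deaths remain instead of 201-205.
- Survival counted from first drug at 45 days: 41-49% fall in 2018, and 100 deaths remain instead of 187.
- Precision for a KPI of 30%, half-width 1.96 x sqrt(0.3 x 0.7 / deaths): 9.0 points at 100 deaths and 8.1 at 124, against 6.6 at 187 and 6.3 at 205.
- The percentage does not move if late treatment is unrelated to survival time. As an illustration with index dates over the whole year and a 12-month median, treatment rates of 40% for deaths before 6 months and 15% after give about 35% under section 5 and 30% under section 3. Rates of 10% and 30% give 14% and 18%, so the shift can go either way.

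**KPIs 15 and 16.** The denominator stays at all patients while 2018 use is lost. If use occurred only close to death, the loss would match the 32-49% above: 20% under section 3 would read 20 x (1 - 0.32) = 13.6% down to 20 x (1 - 0.49) = 10.2%. Earlier use loses less.

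**KPI 11a.** Starts falling in 2018: none if immunotherapy is the first drug; 60/335 = 17.9% or 45/320 = 14.1% at 90 days from index.

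**KPI 6.** If surgery is at index and the drug follows, the last eligible surgery is on day 334 or 319, which leaves at least 30 days within 2017, so nothing is lost. If surgery were spread over all 365 days, 30/365 = 8.2% would lack a full window. With deaths spread evenly over the 30 days, about 4.2% of them would be missed, and 3% would read 2.9%.

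**The case against.** The strongest reply is that the protocol nearly settles the matter itself. Section 3 addresses data outside 2017 explicitly and gives an end date. Section 5.1 lists death and later lines of treatment, and KPI 11b needs more than 6 months of follow-up, so a literal 2017 limit fits poorly with its own section. On a milder reading the section 5 sentence means the 2017 cohort, and the conflict becomes a matter of wording. The study is also descriptive, with no hypothesis test to invalidate.

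Most of this stands as evidence of intent, and section 3 is probably the rule meant. It does not remove the defect. The subject of the section 5 sentence is data, not patients, and it sits in the data-collection section, so a programmer working from it has no cue to go past December 2017.

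Three stronger readings are tempting, but the protocol does not support them:

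- That KPIs 12 and 14 would necessarily be distorted. Only the smaller base, limited to early deaths, is certain. A large upward shift in KPI 12 would need something like one fixed course of treatment for every patient, which the protocol nowhere states.
- That the whole KPI 11b shortfall comes from section 5. At longer lags to immunotherapy, section 3 also falls short of the true value, so the fair comparison is between the two sections.
- That KPIs 15 and 16 would lose a known fraction. Patients with any 2017 use still count, and clustering of use near death is an assumption, particularly for home care.

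**Conclusion.** The two sentences contradict each other, and the one in section 5 is wrong as written. It must be corrected before the query dates are fixed. This is a conflict in the text, not evidence that the extraction will in fact stop at December 2017.

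If section 5 were followed literally:

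- KPI 11b would read less than half its section 3 value: 17-18% against 39.8% for a true 40% if immunotherapy is the first drug, and about 13% against 33-34% at 90 days from index.
- KPIs 12 and 14 would rest on about 100-124 deaths instead of 187-205 (400 patients, 12-month median).
- KPIs 15 and 16 would be too low, by an amount that cannot be fixed from the protocol.
- KPI 11a would be lower to the extent that immunotherapy starts in 2018.
- KPI 6 would change negligibly or not at all.

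The mid-2017 limit for KPI 11b and the loss of 2018 deaths follow from the dates alone. The percentages and counts rest on the assumed uniform dates, fixed lags and exponential survival.

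**What to change.** Replace the section 5 sentence with a rule to this effect: 2017 defines the cohort (index hospitalisation and the drug-treatment criterion of section 3) and any KPI whose own definition names the year (KPIs 3 and 7); all other KPI data follow section 3, to death or 30 June 2018; look-back and etoposide data follow section 4.1. The cost is wording and query dates. No data are needed beyond the cut-off that section 3 already sets.

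Optional and separate, with no bearing on the severity above: even under section 3, first immunotherapy doses after about 29 December 2017 enter the KPI 11b denominator but cannot reach its numerator. That denominator could be restricted to first doses more than 6 months before 30 June 2018, with the number left out reported. By 1/sqrt(1 - share left out), the confidence interval widens by under 1% if immunotherapy is the first drug and by 8-11% at a 90-day lag from index.

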### 5.1 Clinical variables of interest for the study

The only source for clinical information will be administrative databases in all its parts.

[figure not shown]
We will focus primarily on the following set of clinical data:

- Biopsy at diagnosis;
- Presence of metastatic NSCLC at diagnosis;
- Neoadjuvant treatment before lung cancer surgical resection;
- Lung cancer main surgical resection;
- Length of stay in hospital after lung major surgery;
- Main information regarding anti-cancer drug treatments at the first diagnosis and for subsequent lines
- Multidisciplinary team (MDT) meeting discussion;
- Radiotherapy (RT) in the end of life;
- Death;
- Integrated home care utilization;
- Hospice care utilization.

[figure not shown]
### 5.2 Key performance indicators for monitoring care pathway in NSCLC patients

The following key performance indicators (KPIs) will be measured to investigate the appropriateness of NSCLC patient care pathways, with a special focus on the use of immunotherapy.

[figure not shown]
BOZZA - KPI -	
1	
Percentage of patients who performed biopsy within 7 days from the date of examination prescription
 
NUM: Number of patients who performed biopsy within 7 days from prescription; DEN: Total number of patients identified by the algorithm who performed biopsy;

2	
Percentage of mNSCLC patients at diagnosis
 
NUM: Number of patients with metastases (presence of one of the following codes (197*,198*,199*) in all position of diagnosis codes for index hospitalization); DEN: Total number of patients identified by the algorithm;

3	
Percentage of major surgical resections within the year of analysis.
 
NUM: Number of patients who underwent to lung cancer major surgical resection; DEN: Total number of patients identified by the algorithm;

	
To identify major surgical procedures for lung, the following codes of ICD-9-CM classification will be identified:
 
  
 ICD-9-CM coding related to major surgery on lung	
   
 32.01	ENDOSCOPIC EXCISION OR DESTRUCTION OF LESION OR TISSUE OF BRONCHUS	
 
 32.29	OTHER LOCAL EXCISION OR DESTRUCTION OF LESION OR TISSUE OF LUNG	
 
 32.3	SEGMENTAL RESECTION OF LUNG	
 
 32.4	LOBECTOMY OF LUNG	
 
 32.5	COMPLETE PNEUMONECTOMY	
 
 34.6	SCARIFICATION OF PLEURA	
  
	ICD-9-CM coding related to major surgery on lung		32.01	ENDOSCOPIC EXCISION OR DESTRUCTION OF LESION OR TISSUE OF BRONCHUS	32.29	OTHER LOCAL EXCISION OR DESTRUCTION OF LESION OR TISSUE OF LUNG	32.3	SEGMENTAL RESECTION OF LUNG	32.4	LOBECTOMY OF LUNG	32.5	COMPLETE PNEUMONECTOMY	34.6	SCARIFICATION OF PLEURA
ICD-9-CM coding related to major surgery on lung															
32.01	ENDOSCOPIC EXCISION OR DESTRUCTION OF LESION OR TISSUE OF BRONCHUS														
32.29	OTHER LOCAL EXCISION OR DESTRUCTION OF LESION OR TISSUE OF LUNG														
32.3	SEGMENTAL RESECTION OF LUNG														
32.4	LOBECTOMY OF LUNG														
32.5	COMPLETE PNEUMONECTOMY														
34.6	SCARIFICATION OF PLEURA														
4	
Percentage of surgical patients on the total number of patients with exploratory thoracotomy in inpatient setting.            NUM: Total of patients with only exploratory thoracotomy procedure (Cod 34.02);            DEN: Number of surgical patients;            For major surgery, ICD-9-CM codes were selected as reported for KPI 3.            Surgical patients defined as patients who receive any surgical procedure (major and/or explorative)
														
5	
Percentage of patients undergoing neoadjuvant therapy ( CT or CT+RT within 6 months prior to the first major resection date)            NUM: Number of patients who underwent induction treatment as CT or CT+RT in the 6 months prior to surgery;            DEN: Total number of surgical patients;            The algorithm will not be able to identify patients who received neoadjuvant therapy in clinical trials.            For major surgery, ICD-9-CM codes were selected as reported for KPI 3.
														
6	
30-day mortality rate from major surgery            NUM : Number of patients who died within 30 days from major surgery;            DEN: Total number of surgical patients;            For major surgery, ICD-9-CM codes were selected as reported for KPI 3.
														
7	
Percentage of patients discussed in the multidisciplinary team (MDT) meeting at least once in the year of incidence            NUM: Number of patients discussed at least one time in MDT meetings;            DEN: Total number of patients identified by the algorithm;
														
8	
Percentage of patients who performed imaging exams such as MRI, TC and PET within 7 days from MDT meeting            NUM: Number of patients who performed imaging exams within 7 days from MDT meeting;            DEN : Total number of patients discussed in MDT meeting;
														
9	
Average and range of length of stay calculated as the mean difference among date of discharge and date of admission.
														
10	
Average time between biopsy and the first administration of systematic anti-cancer drug (excluded neoadjuvant patients of KPI 5) calculated as the average difference among biopsy and the first date of administration of chemotherapy.            For patients enrolled in experimental clinical trial will not be possible to retrieve information on therapies from administrative database.
														

11	
KPIs on THERAPIES For patients enrolled in experimental clinical trial will not be possible to retrieve information on therapies from administrative database.
 
a) Percentage of patients treated with immunotherapies NUM: Patients with at least one administration of immunotherapy According to Anatomical Therapeutic Chemical Classification System ATC, the following codes will be investigated: L01XC17 nivolumab L01XC18 pembrolizumab L01XC32 atezolizumab
 
DEN: Total number of patients identified by the algorithm who underwent anti-cancer drug treatment for NSCLC, as single or double agent chemotherapy, target therapy etc..(excluded neoadjuvant patients of KPI 5)
 
b) Percentage of patients who underwent immunotherapy for more than 6 months after first dose. NUM: Number of patients who underwent immunotherapy more than 6 months after the first administration; DEN: Total number of patients identified by the algorithm who underwent immunotherapy;

12	
Percentage of patients who underwent anti-cancer drug treatment in the last 30 days of life NUM: Number of patients who underwent anti-cancer drug treatment in the last 30 days of life; DEN: Total number of patients identified by the algorithm who deceased

13	
Percentage of patients who underwent the first administration of systematic anti-cancer drug within 30 days from discussed in MDT meeting NUM: Number of patients who underwent first systematic anti-cancer drug administration within 30 days from MDT; DEN: Total number of patients patients identified by the algorithm discussed in MDT meeting;

14	
Percentage of patients who underwent RT in the last 30 days of life ( excluded palliative treatments single fraction) NUM: Number of patients who performed RT in the last 30 days of life ( excluded palliative treatments); DEN: Total number of patients identified by the algorithm who deceased;

15	
Percentage of patients who underwent at least one Integrated Home Care (IHC) NUM: Number of patients who underwent IHC service; DEN: Total number of patients identified by the algorithm;

16	
Percentage of patients who underwent at least one hospice care NUM: Number of patients who underwent hospice care; DEN: Total number of patients identified by the algorithm;

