##### **4.1 Definition of study groups**

An algorithm will be developed to reliably identify eligible subjects from administrative database SDO. The algorithm will apply specific criteria to patients collected in administrative databases from January 2017 to December 2017. It will be developed as the combination of ICD-9-CM codes with other criteria. Selection of codes and criteria was based on a discussion between senior Oncologists with expertise in lung cancer and the outcome research working group at IRST.

A first data extraction from the administrative database will be performed to identified potential study subjects. These data are related to patients with at least one hospitalization due to diagnosis of malignant tumors of trachea, bronchi and lungs between January and December 2017 using the International Classification of Diseases, 9th EDITION, (ICD-9-CM codes: 162\* in all position of diagnosis codes).

The following criteria will be applied to obtained patients, to exclude prevalence NSCLC cases (incident cases in 2014-2016 period), patients with mesothelioma (cod 163\*) and SCLC patients in order to obtain the correct population.

- Only NSCLC incident cases in 2017 will be considered, excluding prevalence cases that had the same diagnosis in the 3 years before the period of interest (2014-2016). Patients with at least one hospitalization due to diagnosis of malignant tumors of trachea, bronchi and lung according to ICD-9CM 162\* in the 3 years prior to the first index hospitalization on the year of evaluation (2017) will be excluded

- Patients with at least one hospitalization due to malignant tumor different than tumors of trachea, bronchi and lungs (ICD-9CM 140\*-161\* or 163\*- 195\* or 200\* - 208\* or V.10\* excluding V10.11 and V10.12), in the 3 years previous 2017 should be excluded.
- All patients with at least one ATC Code L01CB01
- Etoposide (VP-16) therapy administration in the 180 days following the first hospitalization index will be excluded.

After criteria application, the final population shall include only NSCLC patients.

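### KPI 3 and KPI 7 close on 31 December 2017 for patients who enter throughout 2017, so time to qualify runs from 364 days to none and events falling outside the year are scored as failures

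*Protocol*

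**What the plan says.** All references are to the Protocol.

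- **Windows (Section 5.2).** KPI 3 is the "Percentage of major surgical resections within the year of analysis". KPI 7 is the "Percentage of patients discussed in the multidisciplinary team (MDT) meeting at least once in the year of incidence". The numerator lines of both rows repeat no window.
- **The year (Section 4.1).** Prior cases are excluded relative to the "first index hospitalization on the year of evaluation (2017"), and only 2017 incident cases are kept. Both windows are therefore calendar 2017.
- **Entry (Section 4.1).** The algorithm selects hospitalizations for malignant tumours of "trachea, bronchi and lungs between January and December 2017", so entry is spread over the year.
- **Denominator (Section 5.2).** For KPI 3 it is "DEN: Total number of patients identified by the algorithm", and KPI 7 uses the same wording. No minimum time under observation is required.
- **Data (Sections 3 and 5).** Section 3 states: "All data needed for KPI calculation, even if they fall outside January-December 2017 period, will be collected". It ends collection at death or 30 June 2018. Section 5 limits the data for the primary objective to 2017. The two conflict.
- **Cohort (Section 3).** Section 3 also requires at least one anti-cancer drug treatment during 2017. Sections 4.1 and 4.3 do not repeat this condition.

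**The concern.** The windows are tied to the calendar and entry is not, so patients do not have equal opportunity to be counted. A patient first admitted in late 2017 and resected in early 2018 stays in the KPI 3 denominator and counts as unresected. A patient whose only MDT discussion was in December 2016 or in 2018 counts as not discussed in KPI 7.

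For KPI 3 the induction pathway is exposed in particular. KPI 5 is the "Percentage of patients undergoing neoadjuvant therapy ( CT or CT+RT within 6 months prior to the first major resection date"), so the protocol itself foresees up to 6 months between induction and surgery. A patient who starts induction in autumn 2017 and has surgery in 2018 is in the cohort even under the drug-treatment condition of Section 3, yet is scored as not resected.

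Both indicators are pulled downward for a reason unrelated to whether the procedure was done. They serve a primary objective about appropriateness and quality of care.

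**Working it through.** The protocol gives no KPI value, power or precision figure to reproduce. The 400 patients of Section 7.2 are a feasibility count.

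**Step 1: time to qualify.** Days from index to 31 December 2017 (window as headed) and to 30 June 2018 (end of collection in Section 3):

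| Index date | To 31 Dec 2017 | To 30 Jun 2018 |
|---|---|---|
| 1 Jan 2017 | 364 | 545 |
| 1 Jul 2017 | 183 | 364 |
| 1 Dec 2017 | 30 | 211 |
| 15 Dec 2017 | 16 | 197 |
| 31 Dec 2017 | 0 | 181 |

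**Step 2: share of true events lost.** The protocol gives neither the distribution of index dates nor any lag. Assume index dates uniform over 365 days and one fixed lag of L days from index to event. The event falls after 31 December for the last L index dates, so the share lost is L/365:

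| Lag L (days) | Lost | Captured |
|---|---|---|
| 14 | 14/365 = 3.8% | 96.2% |
| 30 | 30/365 = 8.2% | 91.8% |
| 60 | 60/365 = 16.4% | 83.6% |
| 90 | 90/365 = 24.7% | 75.3% |
| 120 | 120/365 = 32.9% | 67.1% |
| 180 | 180/365 = 49.3% | 50.7% |

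The loss falls on late entrants. For the 92 index dates from October to December, the captured share is (92 − L)/92: 62/92 = 67% at 30 days, 32/92 = 35% at 60 and 2/92 = 2% at 90.

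**Step 3: limits on these figures.** If a share s of resections takes place during the index admission (lag near zero), the KPI 3 loss is (1 − s) × L/365. It lies between 0 and the tabulated value, so the table gives upper bounds for KPI 3. For KPI 7, a sole discussion L days before index is lost by the same formula at the January end of the year.

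**Step 4: size against sampling error (assumed true rates, n = 400).** Observed rate = p × (1 − L/365); 95% half-width = 1.96 × √(p(1 − p)/400).

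- KPI 3, p = 20%: read as 18.4% (30 days), 16.7% (60) or 15.1% (90). The half-width is 3.9 points. The 90-day shift of 4.9 points exceeds it; the 60-day shift of 3.3 does not.
- KPI 7, p = 90%: read as 86.5% (14 days), 82.6% (30) or 75.2% (60). The half-width is 2.9 points, so each of these shifts (3.5, 7.4 and 14.8 points) exceeds it.

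**Step 5: is an equal window observable?** 31 December 2017 + 180 days = 29 June 2018, one day before the Section 3 cut-off. A common window of up to 180 days after index can be observed for every patient, and no event with a lag of 180 days or less is then lost.

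**The case against.** **Section 3 already collects data into 2018.** True, but it collects what the KPIs need, and as headed KPI 3 and KPI 7 need nothing from 2018. Even if the numerators were read without a window and run to 30 June 2018, opportunity would still range from 545 to 181 days.

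**The KPI 7 wording could mean 12 months from diagnosis.** Section 4.1 works in calendar 2017, and 12 months cannot be observed for patients indexed after 30 June 2017 when collection stops on 30 June 2018.

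**The drug-treatment condition removes some of the affected patients.** This stands in part. Under Section 3, a November patient with no drug until January 2018 is not in the cohort. For KPI 7 it may matter more: KPI 13 measures first drug after the MDT meeting, and on that sequence a late patient treated by 31 December would usually have been discussed by then. But Sections 4.1 and 4.3 omit the condition, and the patient who starts induction in 2017 and is resected in 2018 is affected under either cohort definition.

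**The size is conditional.** This stands. Lags and true rates are assumptions, and one fixed lag for everyone is a simplification.

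**Stronger readings.** A reader might infer that late-diagnosed or neoadjuvant patients as a group are misclassified. They are not: only those whose event falls outside 2017 are affected, and the neoadjuvant delay bears on KPI 3, not KPI 7. A reader might also infer that the comparison between sites is shown to be distorted. The loss could differ between sites if work-up time, neoadjuvant use or index dates differ, but the protocol gives no data on any of these.

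**Conclusion.** The point holds. With the windows as headed, staggered entry and an all-patient denominator, time to qualify ranges from 364 days to 0, and patients whose resection or only MDT discussion falls outside 2017 are scored as failures. The windows are fixed in the KPI headings, so this is not a detail left for later specification.

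Under uniform entry and a fixed lag, the loss is about 8% of true events at 30 days, 16% at 60 and 25% at 90. These are upper bounds for KPI 3, and for both indicators they refer to the full algorithm cohort without the Section 3 drug-treatment condition. An unequal effect across sites is possible, not demonstrated. The change should be made before the indicators are calculated.

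**What to change.** 1. Define KPI 3 and KPI 7 over one window counted from the index hospitalization and equal for all patients, up to 180 days after index. For KPI 7, add a stated look-back before index, so that a discussion preceding the admission counts.
2. Reconcile Section 3 (data outside 2017 allowed, collection to 30 June 2018) with Section 5 (2017 only). The fix needs no further collection only if Section 3 prevails; the KPI 7 look-back also needs late-2016 records, which Section 3 permits. State at the same time whether the drug-treatment condition of Section 3 defines the cohort.
3. Align the dependent denominators: surgical patients in KPIs 4 to 6 and MDT-discussed patients in KPIs 8 and 13.

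**Cost.** Two KPI rows change in wording, five dependent rows are aligned, and two sections are reconciled. Events more than 180 days after index are no longer counted, including some resections after long induction that count today. For example, index on 1 February and resection on 25 August 2017 is 205 days. Report as a supplement the KPI 3 count of all resections to 30 June 2018 by index date, so that these remain visible.
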